5.4 CONFOUNDERS

Any baseline differences between clients seen by intervention and comparison teams in demographic or socioeconomic characteristics and mental health condition may act as potential confounders. These will be assessed in the analysis and, if necessary, adjustment made in analyses.

Another potential confounding factor could be that patients will accumulate around the GPs with the most engagement in the study who have the shared eMR (electronic medical record) installed early on. MHS case coordinators will be asked to monitor whether any consumers have changed GPs as a result of the trial and inform the study investigators if this happens. We cannot stop consumers from changing GPs, but we can only monitor if this happens. Our experience with this consumer group is that changing GPs is unlikely unless a consumer is dissatisfied with their existing GP.

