Objectives	
The primary objectives of the SHAReD study are:
 
 1. Does the implementation of an online shared care plan (the intervention) improve the frequency and quality of primary and preventive care received by study participants in intervention sites compared to participants in sites with usual care 3 months after their reported usual shared care ? 
The secondary objectives are:
 
 2. Does the intervention better integrate care between mental health services and general practice compared with usual care 3 months after their reported usual shared care ? 3. Does the intervention improve consumer health risks and service use compared with usual care 3 months after their reported usual shared care? 4. What are the main costs and health outcomes associated with the intervention and usual care situations, is the intervention more cost-effective compared to usual care, and are there any costs avoided (saved) 3 months after their reported usual shared care?
Study design	Pragmatic trial with the unit of randomisation being four of the five Adult Community Mental Health 'Core' Teams in Sydney Local Health District (SLHD). Pairs of teams (matched by service type and consumer population) randomised to early or late intervention 3 months after their reported usual shared care.
Planned sample size	500 consumers and their shared-care GPs
Selection criteria	
Inclusion criteria are:
 
 1. People who are clients of the SLHD Adult Community Mental Health 'Core' Teams in Canterbury, Croydon, Camperdown and Marrickville and the GPs that these consumers nominate. 2. Age: 18+ years 3. Engaged in shared care or willing to commence a shared care arrangement before participating in a baseline survey. 4. Intervention group: Has a GP engaged in shared care who consents to participate in the study and to have the electronic care plan installed. 5. Willing to provide informed consent and willingness to participate and comply with the study requirements. 
Exclusion criteria

	
Unable to give informed consent.
 
Unable to speak English or a language not supported by the study.

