The RPA Virtual Hospital at SLHD will be available across all four teams. It will be used in the intervention for:

1. people who do not have a GP or not able to get to a GP - RPA VIRTUAL will fill the GP role
2. teleconsultations involving the GP, mental health care coordinator (MHC) and the consumer. This will save the MHC going with a patient to the GP.

The tasks for the consumer, the GP and the MHS in the intervention are presented in Figure 1.

[figure not shown]

Figure 1 Intervention flow chart

Context

SLHD has five Adult Community Mental Health 'Core' Teams. The four largest teams will be involved in the study: 2 in Western Sector, 2 in Eastern Sector.

Table 1 Mental health teams in the study

Western Sector Teams	Eastern Sector Teams
Canterbury	Camperdown
Croydon	Marrickville

The SLHD Living Well Living Longer shared care program used the ACI clinical redesign process in partnership with CESPHN to develop a collaborative model of shared care with GPs.¹² This has engaged over 330 GPs in providing shared care to over 1000 PWSMI, 736 of which remain active with the MHS at most recent count. Of those active shared care consumers, 512 have received a verified annual physical health check with their GP.

These innovations require change to existing routines in both MHSs and general practice, facilitated by quality improvement activities led by clinical champions.

Training and support will be provided on using the shared care software to the implementation teams, in collaboration with the existing GP shared care liaison clinicians within Sydney Local Health Service (SLHD)'s MHS, and CESPHN field support staff. Separately they will provide training and support to GP practices upon installing the

shared care software. This training will also address redesign of routine practices and be provided to medical staff, care coordinators and peer support workers. The training and redesign elements will be informed by our previous research providing both training and quality improvement in general practice in the prevention and management of long-term conditions and care of vulnerable populations.^{13,14} This includes the importance of interactive and peer learning. It is also consistent with the education and practice support program of partner CESPNN.

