4. STUDY DESIGN

4.1. DESIGN / STUDY TYPE

This is a pragmatic cluster randomised controlled trial. The unit of randomisation is the team. The teams are four of the five Adult Community Mental Health 'Core' Teams in SLHD (Table 1). Randomisation will be stratified by sector (Eastern and Western): One team from each sector will be randomised to the intervention group, the other team will be allocated to the comparison group. The comparison group Teams will receive the intervention after the 3-month data collection is complete.

As there are only two teams per sector in the study, randomisation will be done by a person independent from the study by flipping a coin.

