- The capacity of the consumer to consent to the research will be assessed his/her mental health care coordinator, who is qualified to judge the capacity of their patients. Where there are any concerns, this will be discussed with the consumer's treating psychiatrist.
- Care coordinators will advise the research team of any changes in the participant's capacity to consent and to participate in the research.
- Care has been taken in the design of the interviews and will be taken in the training of interview staff to ensure that the interview does not increase consumer's discomfort or distress and to ensure that, if this were to occur, that the interview would be stopped and the consumer supported and referred appropriately.

RECRUITMENT OF GPs

1. After a consumer has consented to participate in the study (which includes consent to the research team contacting their GP about study participation), the research team will contact the consumer's GP. The name of the GP and their practice will be confirmed with the consumer.
2. If feasible, a letter from the consumer is posted to the GP informing that the consumer has consented to be in the study and inviting the GP to be in the study (Appendix 15.2). The letter states: *"The research team will contact you shortly or you can contact the Research Manager, [name]"*.
3. The GP contact details are recorded by the MH clinician in an Excel database on the SLHD MS Teams folder and shared with the research team.
 - 3.1 Intervention group: Details of GPs who decline will not be retained after data collection has completed. They will be retained during the data collection period because consumers are known to change GPs and this information is likely to be necessary to follow up.
 - 3.2 Comparison group: Details of GPs who decline but whose consumers consent to participate, will be retained. They will be retained because consumers will receive their usual shared care (no need for the GP to install the electronic care plan), and this information is likely to be necessary to follow up.
4. The research team will use a script when they contact the GPs (Appendix 15.4).

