Mental health service care coordinators who have facilitated consumer recruitment to the study will be invited to express interest in being interviewed via a letter of invitation sent to them by the Principal Investigator, [name] (Appendix 13). The letter of information will include a Participant Information sheet (Appendix 10.3) and consent forms for care coordinators (Appendix 11.4). A similar process to that for consumers will be used to ensure that a broader consumer and Provider perspective on shared care is captured.

11. How will participants be reimbursed for their time and expenses for participation in the study?

Consumers will be reimbursed for their time and expenses participating in the baseline survey, follow-up survey and qualitative interview via a \$20 gift voucher per occasion of participation (maximum \$60 per consumer across the course of the study). This amount was deemed reasonable as the survey is designed to be short in duration and additional travel should not be necessary as interviews are expected to be conducted via telephone, zoom, or face-face at the mental health service.

GPs will be reimbursed for their time and expenses participating in the research study via a \$100 shopping voucher (or cash whichever GP prefers) for participating in each of the following components of the study including 1) Baseline survey (15 min), 2) Follow up survey (15 min), 3) Data extract (just access to computer), 4) INCA installation/training (intervention group now and comparison group 3 months after their usual shared care appointments, i.e., 3 months after 30 June 2023) and 5) Qualitative interview (20-30 minutes). Each GP receives total 5, \$100 payment over the study period.

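### GPs take their arm from the consumer who nominates them, and no rule covers a GP with consumers in both arms, so the contrast may be diluted by an unknown amount

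*Protocol*

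**What the plan says.** Section 4.1 states that "The unit of randomisation is the team" and, on stratification by sector, that "One team from each sector will be randomised to the intervention group, the other team will be allocated to the comparison group".

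GPs come in through consumers. The selection criteria in the synopsis list the four teams, ending "Marrickville and the GPs that these consumers nominate". Under section 5.3 (recruitment of GPs), once a consumer has consented, "the research team will contact the consumer's GP. The name of the GP and their practice will be confirmed with the consumer".

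Section 5.3, item 11, dates the software by arm: "INCA installation/training (intervention group now and comparison group 3 months after their usual shared care appointments". It explains the later date as three months after 30 June 2023. Section 4.1 says only that comparison teams get the intervention once the 3-month data collection is finished. Section 1.1 says the training also covers how practices organise their routine work.

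Section 5.4 discusses consumers gravitating towards GPs who have the software, considers this unlikely, asks coordinators to report it, and concludes: "We cannot stop consumers from changing GPs, but we can only monitor if this happens". Section 5.3 (recruitment of GPs, 3.1), explaining why details of declining GPs are kept, says that "consumers are known to change GPs".

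Table 9 lists three primary outcomes: screening recorded by GPs, prescribing recorded by GPs, and GP advice or referral reported by consumers. The two record-based outcomes use May to October 2023 as the post-intervention period. Provider-reported communication, from the provider survey and interviews, is a secondary outcome.

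**The concern.** The protocol writes of intervention GPs and comparison GPs (section 5.3, Table 6, section 9.3) as if each GP belonged to one arm. That holds only if no GP or practice has enrolled consumers from both. The two teams of each sector are placed in opposite arms, and nothing in the recruitment steps checks whether a newly named GP already has consumers in the other arm.

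A GP with consumers on both sides has no defined place. The installation schedule gives that GP two dates, the GP survey gives no arm to file the answers under, and the comparison consumers are treated by someone already trained. All three primary outcomes depend on what GPs do or record, so any carry-over of changed practice would raise the comparison rate and pull the estimated difference towards zero. The route that section 5.4 does consider, switching, is a different one, and its judgement that switching is unlikely sits awkwardly with the statement in section 5.3.

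The dates raise a second exposure. Comparison GPs may be installed before the period in which their records are counted has ended.

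**Working it through.** **1. Place the passages side by side.**
- Randomised unit: team (4.1).
- How a GP acquires an arm: through the nominating consumer (synopsis, 5.3).
- What follows from the arm: date of installation and training (5.3, item 11).
- Rule for a GP or practice with consumers in both arms: none in the visible text. Section 5.3, item 9, covers a GP who declines. The limitations in 5.5 do not mention contamination. Section 8.2 considers GP and medical centre as random effects, which deals with correlation and does not restore a diluted difference.

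**2. Dates.** Three months after 30 June 2023 is about 30 September 2023. The Table 9 window closes at the end of October 2023. Comparison installation can therefore begin about one month before the six-month window ends.

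**3. Reproduce the planned sample size (4.2, 8.1).** Inputs are 30% against 50%, alpha 0.05 (two-sided reproduces the figure), power 0.80 and design effect 2.

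n per group = (1.96 + 0.8416)² × (0.3×0.7 + 0.5×0.5) / 0.2² = 90.3, so 91, as stated. Doubling gives 182 per group and 364 in total, close to the stated 180 and 360. No allowance for contamination enters.

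**4. Effect of carry-over.** Let c be the share of comparison consumers whose GP is equipped and trained, and f the fraction of the effect that reaches them. Neither is in the protocol, so both are assumed.

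- Comparison rate: a = 0.30 + c × f × 0.20. Difference: d = 0.50 − a.
- Power = Φ( d / √[(a(1−a) + 0.25)/90] − 1.96 ), where 90 = 180/2 is the effective number per arm.

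Worked line for c = 10%, f = 0.5: a = 0.31, d = 0.19, standard error √(0.4639/90) = 0.0718, 0.19/0.0718 − 1.96 = 0.69, power 75%.

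| c | f | Difference (points) | Power at 360 | Total needed for 80% |
|---|---|---|---|---|
| 0 | – | 20 | 80% | 364 |
| 10% | 0.5 | 19 | 75% | 404 |
| 20% | 0.5 | 18 | 70% | 456 |
| 30% | 0.5 | 17 | 65% | 512 |
| 10% | 1 | 18 | 70% | 456 |
| 20% | 1 | 16 | 60% | 584 |
| 30% | 1 | 14 | 48% | 772 |

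If all 400 expected completers are available (effective 100 per arm), power is 84% without carry-over. With f = 0.5 it is 80%, 75% and 70% at 10%, 20% and 30%.

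**The case against.** The protocol does not say that paired teams share GPs, does not call them neighbouring, and gives no overlap figure. A reader might infer heavy sharing from the common sector and from the size of the GP pool: "This has engaged over 330 GPs in providing shared care to over 1000 PWSMI", about 3 per GP. Spreading 250 intervention consumers evenly over 330 GPs gives 1 − (1 − 1/330)^250 = 0.53 as the chance that a comparison consumer's GP also has an intervention consumer. That is a full-mixing ceiling and should not be used as an estimate. It takes a district-wide count not split by team, and it treats every nominated GP as equipped, although a GP must also consent and have an electronic record (4.5, 5.1, 5.2). If half consented (assumed), the ceiling would be about 0.27.

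Carry-over is also limited. The online plan needs both sides: one party creates it, the other joins, and the care coordinator reviews it (6.2). Comparison teams are not yet using it, so what can spill over is mainly the GP's training. The full-effect rows above are therefore an outer bound.

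A reader might also infer that a null result could never be told apart from contamination. The documents do not support that. The consumer's GP is recorded at referral and confirmed (5.3), de-identified platform data are supplied (6.3), and fidelity is assessed (8.2). Overlap can be measured; the visible text simply does not say that it will be.

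Two further points are fair. Item 11 of section 5.3 is a reimbursement list, though it is the only visible text that dates comparison installation. A sensitivity analysis could also sit in a statistical analysis plan that is not shown. But who is installed when, and how a shared GP is classified, are rules of conduct that the protocol has to fix. Figure 2 and the GP recruitment appendices are not shown and might add detail.

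**Conclusion.** The gap is real: arm membership of GPs follows the consumer, timing of the software follows that membership, and the visible text has no way to identify, time or classify a GP or practice serving both arms. The contrast may be diluted; the documents do not show that it is. Under the assumption that 10% to 30% of comparison consumers receive half the effect, the loss is 1 to 3 of the 20 points and power at 360 with design effect 2 falls from 80% to between about 75% and 65%. Those figures depend entirely on the assumed overlap and carry-over.

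Two inconsistencies need no assumption. Sections 5.3 and 5.4 give different impressions of how often consumers change GP. The installation date in 5.3, item 11, also falls before the Table 9 outcome window closes. The point deserves a change because the remedy is cheap and part of it concerns conduct that cannot be repaired at analysis.

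**What to change.** 1. Reconcile section 5.3 (item 11) and section 4.1 with Table 9. State that no comparison-team consumer has an INCA plan opened, and no GP serving only comparison consumers is installed or trained, before the outcome window closes. Say that the first part applies even where the practice already has INCA.
2. In section 5.4, flag every GP and practice with consumers from both arms, using the GP named at referral and confirmed with the consumer. Keep the coordinators' reports of GP changes. Do not rely on the consumer survey for this, since no visible text shows that it records a GP name. Bring the statements on changing GPs in 5.3 and 5.4 into line.
3. In section 8.2, keep the comparison by randomised team as primary and add a sensitivity analysis that excludes flagged practices.
4. For the GP-survey outcome, compare GPs serving one arm only and report mixed GPs separately.

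The cost is wording, one flag derived from data already held, and a somewhat later start for comparison GPs. The sensitivity set will be smaller, and the GP-survey contrast will lose the mixed GPs.

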5.5 STUDY LIMITATIONS

Study limitations may include:

- Inability to conduct RCT at individual level due to practical constraints of doing so.
- Reliance on self-report for some measures.
- Reliability of routinely collected data from general practice clinical records.

6. STUDY PROCEDURES

6.1. STUDY FLOW CHART

[figure not shown]

Figure 2 Study flow chart

6.2. INVESTIGATION PLAN

The schedule of surveys and qualitative interviews with study participants is presented in Table 6.

Table 6 Schedule of participant surveys and interviews

		Baseline survey	3-month after usual shared care survey	3-month after usual shared care qualitative interview
Consumers	Intervention	✓	✓	✓
	Comparison	✓	✓	✓
Carers	Intervention			✓
	Comparison			✓
GPs	Intervention	✓	✓	✓
	Comparison	✓	✓	✓
MHS	Intervention			✓
	Comparison			✓

The schedule of visits and procedures is presented in Table 7.

Table 7 Study visits and procedures

Study procedures	Observation			Treatment					Follow up
	Enrolment via MHS	GP phone contact	Consumer survey interview	MHS creates online shared care plan before GP Visit 1	GP Visit 1 To create/review online shared care plan ideally with MHS	MHS reviews care plan initially and as needed	Other GP visits as required (optional telehealth with MHS)	Annual physical health check by GP	
Invitation to participate	X								
Participant Consent	X								
Telephone/face-face interview			X						X
GP Agrees		X							
Care plan developed				X	X	X			
Care plan implemented and reviewed					X		X	X	

If consumers consent, the research team will approach their GP to participate. If the GP agrees a summary of the consumer's previous care is sent and the GP is assisted to download and install the software for the e-care plan. The GP or the MHS staff create the standard care plan (depending on workload of the GP). If the GP creates the standard care plan, they invite the mental health team to edit or join the plan. If the MHS staff creates the shared care plan, they invite the GP to edit or join the plan. Then, the care coordinator reviews the care plan and makes adjustments to suit the consumer's individual care and include other providers involved in the care. Next, the consumer is invited and attends the GP. At each visit the tasks in the care plan are completed by the GP with or without involvement of the mental health team by telehealth. Results of tests are uploaded into the care plan. The consumer is able to view the care plan but not to edit it. The care coordinator is able to review the care plan and check if tasks have been performed and results of these. Consumer and provider are sent reminder for follow up visits.

6.3. STUDY PROCEDURE RISKS

Confidentiality/privacy of data

Precedence Healthcare, the developers of the INCA software for online shared care plans, have put in place best-practice data storage and encryption procedures for medical data in Australia. This includes the storage of data on Sydney-hosted servers and SSL encryption across all databases, websites, sub-domains and company emails. Furthermore, all participants will sign up to the shared care software's Privacy Policy and Terms of Use which outline the type of information that is provided and how it will be handled throughout the trial to assess this risk themselves when they sign up for the trial. For the purposes of independence, bias minimisation and confidentiality, all consumer data provided by the software owners (from the software platform) to the investigators will be de-identified."

Other risks

Further study risks and their management are described in Table 8.

Table 8 Study risks and their management

Project phase	Description of risk	Risk mitigation strategy
Recruitment	Consumer feels pressured to be involved and/or concerned about consequences for their own treatment or care.	Initial approach at arm's length by mental health staff not involved in the study. Consumer can then elect to participate or not. During the recruitment interview, the research officer will emphasise that non-participation in the study will not impact their relationship with the MHS or their GP.
Recruitment	Inviting consumers to the study will take time for the care coordinators	Consultation meetings have been conducted with mental health staff to ensure their role is acceptable and not overly burdensome
Recruitment	There could be a variety of reasons why a GP may choose not to participate, such as time commitment and variability of PC skills and having to learn to use a software programme.	The trial is based upon our experience of working with GPs to install the same software package (different shared care template) for working with cancer specialists and their cancer patients. This experience identified that the software was easy to use and worked seamlessly with existing clinical software. In fact, it saved time for the GPs as they no longer needed to send letters or faxes to specialist services. Even so, training was provided (and will be provided in this study) by the research team and the software company. In addition, a position has been funded to ensure GPs are adequately supported to use the new software.
Interviews	Consumer/carer research participant feels uncomfortable about engaging in the interview.	Consumer reminded that they can withdraw at any stage or take a break.

Interviews	Emotional responses activated during the interview	
If participants become distressed during the interview, researchers will provide basic support and inform the care coordinator that the consumer was feeling distressed and might need follow up. If this happens out of hours, the researcher will ask the consumer if there is somebody they should call who can provide support e.g., support worker, GP or carer. If the researcher is concerned about a participant's safety out of hours, they will contact the mental health line [name].
 
Support information is also provided on the PISCF.

Intervention	Consumer feels uncomfortable with information being shared between health care providers or participating in consultations via telehealth	Participants are reminded that participation in shared care and/or telehealth consultations is voluntary and they may withdraw at any time.
Intervention	Care plan does not meet all consumer's needs or their condition becomes more acute.	Consumers can access the care plan and ask their GP or the care coordinator to make changes to add additional roles or actions. GPs are informed how they can quickly escalate care if the consumer's condition becomes more acute or unstable.
Intervention	Adverse event due to a task in the care plan being missed	
Care coordinator will regularly review incomplete care plan tasks.
 
Any adverse event thought to be associated with tasks not completed in the care plan will be regularly reviewed by an independent safety and monitoring committee.

Independent Safety and Monitoring Committee

Given the nature of the intervention and the short duration of the trial adverse events are unlikely. However, in case an adverse event does arise as a result of the intervention or the data collection, an Independent Safety and Monitoring Committee (ISMC) will be established with three people to monitor adverse events linked to the trial.

The Project Steering Committee will report to the ISMC via an online meeting if an adverse arises or, if not, every 6 months. Adverse events will be identified via the SLHD incident management system (IMS) and GPs in the intervention arm of the trial.

About ten adverse events occur each week across the five mental health teams in SLHD. Two of these teams will receive the intervention so less than five adverse events might normally occur. These events are reported to and managed by the SLHD IMS. [name], Principal Investigator and Director of Clinical Services (SLHD Mental Health) will receive weekly reports of adverse events and identify those consumers who are enrolled in the intervention arm of the trial. He will review those reports to ascertain if the incident might be related to the trial. This might require some enquiries to be made by [name]. If, in his professional judgement, he thinks there is any possibility that the incident was related to the intervention, he will then refer it to the ISMC for discussion and direction. A meeting would be scheduled for within a week. In the meantime, the SLHD normal process for incident management will also occur.

GPs in the intervention arm of the trial will be asked (via the GP Participant Information Sheet, Appendix 10.2) to notify the care coordinator of any adverse events related to the trial. The care coordinator will enter an IMS+ notification that goes through the above process.

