9.2 Consumer quantitative interviews

Survey interviews will be conducted with both intervention and comparison consumers at baseline and 3 months after their usual shared care (or 30 June 2023 if they did not have a shared care plan). The interview schedule components and their sources are summarised in Table 9.

Table 10 Sources of questions in the consumer survey

Outcomes	Source of questions
Consumer-reported advice/referral from GP for smoking cessation, diet and physical activity in last 6 months	Questions developed by CPHCE in previous research ^{32,33}
Consumer assessment of extent to which providers (MH & GP) are working to a common care plan in last 6 months	Question developed by CPHCE, informed by research on interprofessional teamworking in primary and community care settings ³⁴
Health literacy (Feeling understood and supported by healthcare providers)	Health Literacy Questionnaire (HLQ) (Domain 1) ³⁵
Current health risk behaviours	Questions developed by CPHCE
Absolute Cardiovascular Disease Risk	Australian Absolute Cardiovascular Disease Risk ³⁷
Diabetes risk	AUSRISK ³⁸
Quality of life	EQ5D-5L ^{28,29}
Costs	Out-of-pocket costs

Accommodation of mental illness: Interviews will be usually conducted by telephone or video conferencing. Carers or support workers will be asked to assist if the participants agree. The interview questions will use plain English and graphic images. Where participants are judged by treating staff to be unable to understand or answer questions remotely the interviews will be conducted in person, with arrangements to ensure the safety of the consumer and research team. In person interviews will be conducted in a location such as health service and respecting social distancing in accordance with the COVID-19 plan of the SLHD. Carers or support workers will be asked to assist if the participant wishes.

The study procedure is flexible allowing interviews to be postponed if the participant is distressed or acutely ill. If participants become distressed during the interview, researchers will provide basic support and inform the care coordinator that the consumer was feeling distressed and might need follow up. If this happens out of hours, the researcher will ask the consumer if there is somebody they should call who can provide support e.g., support worker, GP or carer. If the researcher is concerned about a participant's safety out of hours, they will contact the mental health line [name].

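### The safety committee is shown only intervention-arm incidents that one investigator thinks possibly related to the intervention, so it cannot compare incidents with usual care

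*Protocol*

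**What the plan says.** All of this is in protocol section 6.3, under the Independent Safety and Monitoring Committee, unless another place is named.

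- **Remit.** The ISMC is set up "in case an adverse event does arise as a result of the intervention or the data collection".
- **Sources.** "Adverse events will be identified via the SLHD incident management system (IMS) and GPs in the intervention arm of the trial".
- **Selection by arm.** The Principal Investigator, who is also Director of Clinical Services for the mental health service, "will receive weekly reports of adverse events and identify those consumers who are enrolled in the intervention arm of the trial".
- **Entry to the committee.** If "he thinks there is any possibility that the incident was related to the intervention, he will then refer it to the ISMC". A meeting is then arranged within a week, and the district's ordinary incident management runs in parallel.
- **GP route.** Intervention-arm GPs are asked "to notify the care coordinator of any adverse events related to the trial". The coordinator logs the event in the incident system, and it follows the same path.
- **Background rate.** The district puts its usual load at about ten incidents a week over five teams. For the trial it concludes: "Two of these teams will receive the intervention so less than five adverse events might normally occur".
- **Table 8.** Care coordinators check for incomplete care-plan tasks. The committee reviews events believed to be linked to such tasks.

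Elsewhere, section 9.2 states: "Survey interviews will be conducted with both intervention and comparison consumers at baseline and 3 months after their usual shared care". Sections 4.4, 7 (Table 9) and 8.2 make ED use and hospitalisation a secondary outcome, measured in both groups.

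**The concern.** The raw material for a two-arm view of safety already arrives each week, because the incident report is not restricted to the intervention teams. The process then discards the comparison arm when consumers are matched, and applies a relatedness judgement before the committee sees anything.

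Two things are lost:

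- **A comparison.** Incidents are common in this population whether or not there is a trial. Judging single cases against a steady background is a weak way to notice that a background-type event has become more frequent. The harm named in Table 8, an event that follows a missed care-plan task, may look like an ordinary incident.
- **Independence.** Relatedness is decided by one person who knows the allocation and holds a senior post in the service delivering the intervention. The committee cannot check events that were not referred to it.

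The process also does not fit its own remit. Harm from data collection is covered, comparison-arm consumers are interviewed too, and Table 8 lists distress at interview as a risk. Yet those consumers are never matched to the incident report, and the referral test names only the intervention.

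At stake is how much weight a statement of no safety concern could carry. Section 1.2 plans roll-out across the district if the trial succeeds.

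**Working it through.** **1. Who can reach the committee**

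| Step | Intervention arm | Comparison arm |
|---|---|---|
| Incident recorded in the district system | Yes | Yes |
| In the weekly report to the Principal Investigator | Yes | Yes; no team restriction is stated |
| Matched to enrolled consumers | Yes | No step |
| Reported by GPs | Yes, if related to the trial | No step |
| Referred to the ISMC | If possibly related to the intervention | No step |
| Surveyed, so exposed to data collection (Table 6, section 9.2) | Yes | Yes |

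The comparison arm drops out at matching, not at recording. The test also narrows along the way: the remit covers intervention or data collection, the investigator's review asks about the trial, and referral asks only about the intervention.

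**2. The protocol's own figure**

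10 incidents per week × 2/5 teams = 4.0 per week, which agrees with the stated figure of fewer than five. This counts all clients of two teams, not enrolled consumers, so it cannot serve as a control rate for the trial.

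**3. What an arm-level count would contain**

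Inputs: caseload of 278 to 448 per team (section 4.5); 500 consumers planned (section 4.2).

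Assumptions:
- 250 are enrolled per arm.
- Incidents are spread equally over teams and in proportion to caseload.
- The period is 26 weeks (May to October 2023). This is the record-extraction window in Table 9; the protocol states no safety-monitoring period.

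Enrolled fraction: 250/(2 × 448) = 28% to 250/(2 × 278) = 45%. These are outer bounds, because they put both teams of an arm at the same extreme.

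Expected incidents per arm with no effect:
- 4 × 26 = 104 in two teams
- 104 × 250/896 = 29.0
- 104 × 250/556 = 46.8

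**4. What a two-arm count could show**

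With e expected events in the comparison arm, rate ratio RR, Poisson counts and a two-sided 5% test:

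SE = √(1/(e·RR) + 1/e); power = Φ(ln RR / SE − 1.96)

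| RR | e | SE | ln RR / SE | Power, no clustering |
|---|---|---|---|---|
| 1.5 | 29.0 | 0.240 | 1.69 | 39% |
| 1.5 | 46.8 | 0.189 | 2.15 | 57% |
| 2.0 | 29.0 | 0.227 | 3.05 | 86% |
| 2.0 | 46.8 | 0.179 | 3.87 | 97% |

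The protocol assumes a design effect of 2 for its sample size (sections 4.2 and 8.1). Borrowed here, it halves the information. That equals running the same calculation over 13 weeks: power becomes about 22-33% for a 1.5-fold rise and 58-78% for a doubling.

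Under the written process the comparison-arm count is never made, so no such contrast exists at any size of effect.

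**The case against.** The best defence is proportionality. The intervention puts an existing paper care plan online with its content kept the same (section 1.1), and the protocol expects adverse events to be unlikely. The committee is there to look at events linked to the trial; it was not set up to compare rates. The referral threshold is low, since any possibility of a link is enough. The Steering Committee reports to the ISMC every six months even if nothing arises. A two-arm table would also often miss a moderate excess.

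Much of this stands, and it rules out several stronger readings that a reader might infer:

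- *Comparison-arm incidents go unrecorded.* They do not. The incident system covers every team; the events are recorded but not matched to trial participants. Only the GP route is confined to one arm at source.
- *No excess of harm could be seen anywhere in the trial.* Too strong. ED visits and hospitalisations are measured in both groups and compared, with pre-intervention and same-season reference periods. An excess there could appear in the final analysis. Incidents that lead to neither have no comparison.
- *Harm from missed tasks would go undetected.* Not supported. Table 8 gives the care coordinator a regular check of incomplete tasks and the ISMC a review of events thought linked to them. The weakness is that the link must first be suspected.
- *A table by arm would reveal a modest rise.* The power figures say it usually would not. Planned enrolment may also be optimistic: the version 11 entry in the amendment log refers to a reduced sample, which would lower the counts further.

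What the defence does not answer is the mismatch with the remit. A low threshold still leaves one unblinded, non-independent person deciding what the committee sees. The protocol does not say that the six-monthly report contains unreferred events or counts by arm.

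**Conclusion.** The concern holds for the committee's view of safety, and no further. As section 6.3 is written, the ISMC sees only intervention-arm incidents that one investigator thinks possibly related to the intervention. It never sees comparison-arm events, cannot compare incidents with usual care, and has no route to comparison-arm harm from data collection, although that falls within its remit. These conclusions rest on the text alone.

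The size is illustrative. It depends on 250 enrolled per arm, incidents in proportion to caseload, and 26 weeks. On those assumptions about 29 to 47 incidents per arm would occur by background alone. A two-arm table could show a large excess but would not reliably detect a 1.5-fold one. The case for change is therefore mainly like-for-like ascertainment and independent review, with detection of a large excess as a secondary gain.

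**What to change.** Amend section 6.3 as follows:

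1. From the same weekly report, match incidents to enrolled consumers in **both** arms.
2. Give the ISMC the full listing and counts by arm, with the number enrolled and the time at risk in each arm.
3. Record relatedness, separately to the intervention and to data collection, as an assessment that the committee can review. Do not use it as the condition for entry to the listing.
4. Show GP-notified events on a separate line, because they come from one arm only and would bias a pooled count.
5. Keep the existing prompt referral of possibly related events.
6. State that the table by arm is descriptive and has low power for a moderate excess.

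The cost is one extra match per week on a report already produced, a longer listing for the committee, and an ethics amendment, which section 11.3 requires before the change takes effect. If past weekly reports have been kept, which the protocol does not say, the match could be made once for the whole period.
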